5.2 Analysis Sets

The following analysis sets are defined for this study:

- Full Analysis Set (FAS): This analysis set consists of all subjects who received at least one complete infusion of SBC-102 in the extension study, and have at least one post-treatment measurement in the extension study. This analysis set will be used for analysis of efficacy, PD, and patient health outcomes data.
- Safety Analysis Set (SAFETY): This analysis set consists of all subjects who received any amount of SBC-102 in the extension study. Note: if the FAS and SAFETY consist of the same subjects, then results will be reported as "Full Analysis Set" results, and separate displays for the Safety Analysis Set will not be generated. **Per-Protocol Set (PPS):** This analysis set will consist of all subjects in the FAS who have no protocol deviations that could potentially confound the interpretation of serum transaminase or lipid results.
 - The list of subjects to be included in the per-protocol analysis set will be determined before database lock (i.e. locking of data elements for analysis). If all subjects in the FAS are also in the PPS, then separate analyses for the PPS will not be performed.
- **Pharmacokinetic (PK) Analysis Set:** This analysis set will include all available SBC-102 serum concentration data for subjects who receive at least one complete infusion of IMP in the extension study and will be used for all PK analyses.

5.3 Handling of Missing Data

All data will be analyzed as they were collected in the database. Missing data generally will not be imputed using statistical or manual methods.

6. STUDY SUBJECTS AND DEMOGRAPHICS

6.1 Subject Disposition and Withdrawals

The frequency and percentage of subjects who completed or prematurely discontinued participation in LAL-CL04, will be presented by dosing cohort and overall. A listing, sorted by cohort and subject number, including dose of SBC-102 first administered on the LAL-CL04 study, age, gender, date of informed consent, date of first dose of SBC-102 in the LAL-CL01 study, date of the first dose of SBC-102 in the LAL-CL04 study, date of completion or premature discontinuation from the LAL-CL04 study, whether the subject completed the study or terminated early along with any reason for early termination, and inclusion in the various analysis sets will be provided for all subjects.

6.2 Protocol Deviations

Protocol deviations will be listed by subject, as applicable.

6.3 Demographics and Other Baseline Characteristics

Descriptive summaries for subjects in the Safety Analysis Set and data listings for all subjects, of demographic and other baseline characteristics will be presented by dosing cohorts and overall. The following data will be included:

- Demographics (age, gender, race, ethnicity).
- Investigator and investigational site locations (data listing only).
- Height, weight and BMI (derived as (weight in kg)/(height in m)².
- Medical history as reported in LAL-CL04
- Summaries of lipid-lowering medications will be provided.
- Years since LAL diagnosis and age at LAL diagnosis as reported in LAL-CL01.
- Frequency of abnormal transaminases at the LAL-CL04 Baseline.
- Physical examination at LAL-CL04 Baseline, including clinical significance of findings, size and characteristics of the liver, spleen and lymph nodes, and palpability of the tibialis and pedis pulse.

Body Mass Index (BMI) will be summarized as both continuous variable and as a categorical variable with values of Underweight (<18.5), Normal (18.5-24.9), Overweight (25.0-29.9), and Obese (\geq 30). Abnormal transaminases (at Baseline) are defined as ALT or AST at Baseline is greater than 1.5×ULN. The LAL diagnosis information will be obtained from study LALCL01

from the manual review of medical history data in "Gastrointestinal System" subcategory conducted in that study.

Prior medications/therapies, as reported in LAL-CL04 will be coded using the World Health Organization (WHO) Drug Dictionary, and will be tabulated and listed overall and by dosing cohort.

Medical history and physical examination will be summarized by body system. Details will be listed for all subjects.

7. EFFICACY ANALYSES

Liver and spleen volumes by magnetic resonance imaging (MRI) will be summarized as multiples of normal (where normal is defined as 2.5% of body weight for liver and 0.2% of body weight for spleen). Analysis of efficacy endpoints will include a summary of observed values, absolute change and percent change from baseline for each post-baseline time point in liver and a listing for spleen fat content by multi-echo gradient-echo MRI and H magnetic resonance spectroscopy (MRS) (if available). The protocol also specified analysis of liver cholesteryl ester signature by ¹³C-magnetic resonance spectroscopy, if feasible; the test proved infeasible at participating sites. MEGE and MRS liver fat content will be summarized for the right lobe of the liver; both right and left lobe liver fat content will appear in listings. Descriptive statistics along with 95% CIs will be displayed by dosing cohort and overall. Descriptive pvalues based on the Wilcoxon sign-rank test, unadjusted for multiplicity, may be presented as an assessment change from baseline relative to the observed variability in these measures. These p-values are not considered confirmatory.

An assessment of hepatic histopathology will also be conducted in those subjects who agree to an optional liver biopsy. Biopsy results will be provided in listings and may be summarized if sufficient data are available. ADA data will be listed.

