Criteria for Evaluation	Efficacy Efficacy assessments will include change and/or percent change in liver and spleen volumes by magnetic resonance imaging (MRI), liver and spleen fat content by MRI and ¹ H-magnetic resonance spectroscopy (MRS) (if available), and liver cholesteryl ester signature by ¹³ C- MRS (in a subset of subjects receiving treatment at sites with access to this imaging technology). Histologic assessment of liver disease will be evaluated in subjects who agree to an optional liver biopsy. The effect of ADAs on the efficacy of sebelipase alfa will also be explored.
	Pharmacodynamics Pharmacodynamic endpoints will include change in serum transaminases, serum lipids, and acute phase reactants (e.g., serum ferritin). The effect of ADAs on the PD of sebelipase alfa will also be explored.
	Exploratory disease-related biomarkers, which may be identified based on emerging information from the sebelipase alfa development program and scientific literature, will be analyzed by changes or percent changes from baseline.

	Health-Related Quality of Life (HRQOL) Outcomes
	Health-Related Quality of Life measures will include changes in scores for the 36-item Short Form Health Survey (SF-36 [®]), Functional Assessment of Chronic Illness Therapy (FACIT)-Fatigue scale, and Chronic Liver Disease Questionnaire (CLDQ). Pharmacokinetics
	PK parameters will include maximum observed serum concentration (C_{max}), minimum observed serum concentration (C_{min}), area under the serum concentration-time curve from time zero extrapolated to infinity (AUC _{inf}), terminal elimination half-life ($T_{1/2}$), apparent serum clearance (CL), and steady state volume of distribution (V_{ss}). The effect of ADAs on sebelipase alfa PK will also be explored.
	Sample size is based on the estimated total enrollment in study LAL-CL01, and assumes that all subjects treated in that study will be eligible and willing to participate in this extension study.

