8.7.3 Other Safety Data

Observed measurements and changes from baseline to study timepoints in vital signs (blood pressure, heart rate, respiratory rate, and temperature), and 12-lead ECG parameters will be summarized. Listings of abnormal findings/values for physical examinations, vital signs, and ECGs will be presented, as appropriate.

Concomitant medication/treatment data will be coded using the WHO-DRUG dictionary. All data will be listed, and the number and percentages of subjects receiving each concomitant medication/treatment will be tabulated.

Page **48** of **76**

8.8 Efficacy, Pharmacodynamic, and Patient Health-Related Quality of Life (HRQOL) Outcomes Analyses

Data will be presented for subjects in the Full Analysis Set. All data will be presented by study visit in subject data listings. Observed measurements and changes or percent changes from baseline to study timepoints in liver and spleen volumes and liver and spleen fat content, liver cholesteryl ester signature, serum transaminases, plasma lipids, and acute phase reactants (e.g., serum ferritin) will be summarized overall and by dosing regimen. The percentage of subjects with abnormal transaminases at each timepoint will also be summarized overall and by dosing regimen. Scores and changes from baseline to study timepoints for the SF-36[®], FACIT-Fatigue, and CLDQ will be summarized.

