Appendix A: Schedules of Assessments

Schedule of Assessments: Screening through Week 24*

	Concening	Week	Week	Week	Week	Week	Week	Week	Week	Week	Week	Week	Week	Week	Week
	Screening	1	2	3	4	6	8	10	12	14	16	18	20	22	24
	Day -14 to	±2	±2	±2	±2	±4	±4	±4	±4	±4	±4	±4	±4	±4	±4
Assessments	Day -1	days	days	days	days	days	days	days	days	days	days	days	days	days	days
Informed Consent	Х														
Inclusion/Exclusion Criteria	Х														
Medical History	Х														
Health-Related Quality of Life ¹	Х								Х						Х
12-lead ECG	Х								XP						
Physical Examination ²	Х				X ^P				XP						
Pregnancy Test ³	X ⁸				XP		XP		XP		XP		XP		XP
Clinical Laboratory Tests ⁴	X ⁸				XP				XP						XP
Liver and Lipid Panels	X ⁸	XP			XP		XP		XP		XP		XP		XP
Coagulation Tests ⁴	X ⁸	XP			XP				XP						XP
Anti sebelipase alfa Antibody	Х				X ^P		XP		XP		X ^P		XP		XP
Serum and Urine Exploratory	v				vP		vP		vP		vP		vP		vP
Biomarker Collection	~				^		^		^		^		^		^
PK Profile ⁵															Х
Abdominal MRI/MRS ⁶	Х							Х							Х
Vital Signs ⁷		Х	Х	Х	Х	Х	Х	Х	Х	Х	Х	Х	Х	Х	Х
Sebelipase alfa Infusion		Х	Х	Х	Х	Х	Х	Х	Х	X ⁹	Х	Х	Х	Х	Х
Adverse Events							Со	ntinuous							
Concomitant Meds/Therapies		Continuous													

* All visits will be calculated from Week 1: consecutive infusions must be administered at least 7 days apart.

Pre-dose

Includes SF-36, FACIT-Fatigue, and CLDQ.

² Physical examination will include measurement of weight (height only at screening), assessment of liver and spleen size, lymphadenopathy and arterial disease.

Serum pregnancy test will be performed at screening. Urine pregnancy tests will be performed at all visits thereafter.

Clinical laboratory tests include CBC/hematology, serum chemistry, acute phase reactants and urinalysis. Coagulation tests will be performed at screening and, if results are abnormal, tests will be repeated until normal.

⁵ Pre-dose, 10, 15, 20, 40, 60, and 90 minutes during the infusion, at the end of the infusion, and at 5, 10, 20, 30, 40, 60 and 120 minutes after the end of infusion.
 ⁶ An MRI and ¹H-MRS (if available) will be performed for all subjects. ¹³C-MRS will also be performed for subjects enrolled at sites with access to this imaging

modality.

⁷ Vital signs will be measured pre-dose, every 30 (±10) minutes during the infusion, and from 0 to 4 hours post-infusion.

⁸ Results must be reviewed prior to the start of dosing in the extension study.

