2.2.2 Efficacy Endpoints

The following efficacy measures will be utilized to investigate the effect of SBC-102 on hepatic dysfunction in LAL Deficiency

- Liver and spleen volumes by magnetic resonance imaging (MRI)
- Liver and spleen fat content by multi-echo gradient-echo MRI and ¹H- magnetic resonance spectroscopy (MRS) (if available)

• Histologic assessment of liver disease by biopsy in subjects who agree to the optional procedure.

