16. APPENDICES

16.1 Calculation of Multiples of Normal for Liver and Spleen Volume

Multiples of Normal (MN) are derived by determining the expected "normal" weight of a specific organ based on body weight.

- Liver: 2.5% of body weight in kg gives the expected "normal" liver weight in liters;
- Spleen: 0.2% of body weight in kg gives the expected "normal" spleen volume in liters

For example: a 50 kg subject would have an expected "normal" liver volume of 1.25 liters (0.025*50=1.25) and an expected "normal" spleen volume of 0.10 liters (0.002*50=0.1). The patient's observed organ volume is then divided by the expected "normal" volume. Values of MN >1.0 indicate an organ volume which is larger than the expected normal volume.

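### SAP 7 names only weight-scaled multiples of normal for liver and spleen volume, leaves the weight undefined, and does not declare the departure from the protocol's volume change

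*SAP*

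**What the plan says.** **Protocol.** The synopsis lists as an efficacy assessment "change and/or percent change in liver and spleen volumes by magnetic resonance imaging (MRI". Section 8.8 summarises, overall and by dosing regimen, "Observed measurements and changes or percent changes from baseline to study timepoints in liver and spleen volumes and liver and spleen fat content". Neither place mentions scaling to body weight.

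**SAP.** Section 2.2.2 lists the endpoint without a scale: "Liver and spleen volumes by magnetic resonance imaging (MRI". Section 7 then sets one: "Liver and spleen volumes by magnetic resonance imaging (MRI) will be summarized as multiples of normal". The reference is a fixed share of the subject's weight, 2.5% for the liver and 0.2% for the spleen. The next sentence in Section 7 covers observed values, absolute change and percent change. It opens with efficacy endpoints in general but goes on to name only liver and spleen fat content. Section 16.1 gives the divisor for the liver ("2.5% of body weight in kg gives the expected" normal value) and the matching 0.2% rule for the spleen, with no visit attached to the weight. None of the six items in Section 14, the list of changes from the protocol, concerns organ volume.

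**Weight collection.** Under Protocol Section 5.1.5, weight is taken at every physical examination. The Appendix A footnote agrees: "Physical examination will include measurement of weight (height only at screening), assessment of liver and spleen size, lymphadenopathy and arterial disease".

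**The concern.** Organ volume is the first efficacy measure listed in both documents, and the trial has no control arm. Change from baseline therefore carries all the information on this measure. Body weight in an adult is itself a post-baseline variable. If it enters the divisor at each visit, the summarised change combines what the organ did with what the subject's weight did, and a table of multiples alone cannot separate the two. Weight gain would look like a smaller organ and weight loss like a larger one.

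The SAP names no summary in litres that would allow the separation. It also does not tell the programmer which weight to use, or what to do at an MRI visit with no weight. SAP Section 5.3 says missing data generally will not be imputed, so it supplies no rule for that case.

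**Working it through.** **1. The SAP's own example.** For a 50 kg subject, the expected liver is 0.025 × 50 = 1.25 L and the expected spleen is 0.002 × 50 = 0.10 L. Both match Section 16.1.

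**2. Formula.** Let c be 0.025 or 0.002, V the volume and W the weight. The multiple is M = V/(cW). If volume changes by a fraction v and same-visit weight by a fraction w, then

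percent change in M = (1+v)/(1+w) - 1.

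The constant c cancels, so the result is the same for liver and spleen. If W is held at baseline, percent change in M equals v exactly.

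**3. Constant volume (v = 0), same-visit weight.** The weight changes are assumed.

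| Weight change | Percent change in multiple |
|---|---|
| -10% | 1/0.90 - 1 = +11.1% |
| -5% | 1/0.95 - 1 = +5.3% |
| +5% | 1/1.05 - 1 = -4.8% |
| +10% | 1/1.10 - 1 = -9.1% |

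Two illustrations with assumed constant organs:

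| Weight | Liver 2.0 L | Spleen 0.30 L |
|---|---|---|
| 45 kg | 2.0/1.125 = 1.778 | 0.30/0.090 = 3.333 |
| 50 kg | 2.0/1.250 = 1.600 | 0.30/0.100 = 3.000 |
| 55 kg | 2.0/1.375 = 1.455 | 0.30/0.110 = 2.727 |

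**4. A true 10% fall in volume (v = -0.10).** If weight also falls 10%, the multiple shows 0.90/0.90 - 1 = 0.0%. If weight is stable it shows -10.0%. If weight rises 10% it shows 0.90/1.10 - 1 = -18.2%. In litres, or with baseline weight, all three show -10.0%.

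**5. Effect on a group mean.** With the maximum of 9 subjects, one subject at +10% weight and constant volume moves the overall mean percent change by 9.1/9 = 1.0 percentage point. The full 9.1 points would need a 10% gain in every subject.

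**6. Which MRIs have a scheduled weight (Protocol Appendix A).** Physical examinations are at Screening and Weeks 4, 12, 38 and 52, then four times a year.

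| MRI visit | Scheduled weight at that visit? | Nearest scheduled weights |
|---|---|---|
| Screening | Yes | – |
| Week 10 | No | Week 12 (2 weeks after), Week 4 (6 weeks before) |
| Week 24 | No | Week 12 (12 weeks before), Week 38 (14 weeks after) |
| Week 52, then yearly | Yes | – |

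**The case against.** A reader might infer that change in litres will go unreported and that weight change over five years will appear as organ change. The documents do not support a reading that strong, for these reasons:

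- **Reporting.** Section 7 does not say the multiple is the sole output. SAP Section 4.3 says analyses identified in the protocol will be performed, and Section 14 does not withdraw the volume summary. SAP Section 5.1 puts all data in listings, so litres should be visible by subject. The change-from-baseline sentence in Section 7 could be read to include volume.
- **Artefact.** The SAP never says that same-visit weight is used. With baseline weight the artefact disappears from percent change.
- **Timing.** Only two early MRIs lack a scheduled weight, and Week 10 is within two weeks of one. Every MRI from Week 52 on has one. Protocol Section 6.5.1 also allows for unscheduled weights.
- **Size and importance.** No weight-change data are given. Efficacy is a secondary objective, no formal tests are planned, and scaling to body size puts adults of different size on a common footing. The five years is the protocol's figure; SAP Section 3.1 says up to three.

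All of this stands as a limit on the claim, but it does not close the gap. A listing is not the summary that Protocol Section 8.8 promises. A general clause in Section 4.3 is weak instruction when Section 7 names one specific scale. Unscheduled weights are provided for dose calculation and are not tied to MRI visits. The undefined divisor is a gap under either reading.

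**Conclusion.** The point holds in a limited form. Multiples of normal are the only summary scale that the SAP names for liver and spleen volume. That departs from the protocol's observed volume and its change, Section 14 does not declare it, and the weight in the divisor is undefined.

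Any bias is conditional. It is zero with baseline weight. With same-visit weight, which is the natural reading of Section 16.1, a subject with constant volume shows -9.1% for an assumed 10% weight gain and +11.1% for an assumed 10% loss. Whether weight moves by that much in this cohort cannot be known from the documents. The missing scheduled weight affects Weeks 10 and 24, which are the only post-baseline MRIs before Week 52.

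The analyses are descriptive and efficacy is secondary, so this threatens no formal conclusion. It should still be corrected, because the stated scale can give a weight-driven change, whereas litres cannot and are the protocol's own endpoint.

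**What to change.** 1. **SAP Section 7:** summarise liver and spleen volume in litres as observed value, absolute change and percent change from baseline, with 95% CI, by cohort and overall. Keep the multiples of normal beside it.
2. **SAP Section 16.1:** state whether the divisor is baseline or same-visit weight. If same-visit, give the rule for Weeks 10 and 24, for example the nearest scheduled weight or the last one before the scan.
3. **SAP Section 14:** record that the multiples of normal are a scale added to the protocol's volume analysis.

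Litres are already the numerator, so no new data, visits or subjects are needed. The cost is one more table and a few sentences, and nothing is lost by making the change.

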8. PHARMACOKINETIC ANALYSES

A secondary objective of this study is to characterize repeat-dose pharmacokinetics of SBC-102 delivered by IV infusions [pre and post infusion at Weeks 24, 52, and 104].

Pharmacokinetic parameter estimates for each subject are derived from serum concentration variables.

8.1 Plasma Concentration Data

8.1.1 PK Serum Sample Collection Times

PK samples for measurement of SBC-102 serum levels at Weeks 24, 52, and 104/end of study will be collected:

- Immediately pre-dose (within 30 minutes of the start of the infusion).
- At 10(±1), 15(±1), 20(±1), 40(±2), 60(±2) and 90(±2) minutes from the beginning of the infusion and at the end of the infusion (approximately 120 minutes).

At $5(\pm 1)$, $10(\pm 1)$, $20(\pm 1)$, $30(\pm 1)$, $40(\pm 2)$, $60(\pm 2)$ and $120(\pm 2)$ minutes after completion of the infusion.

8.1.2 PK Serum Sample Elapsed Time

The elapsed time from the start of the infusion to the sampling time will be calculated from the recorded clock time. It will be used to characterize each sample in data listings and for PK parameter estimation. However, the scheduled times will be used to summarize concentration data and mean figures. These new elapsed scheduled times would only be used for the post infusion times. They would add the infusion time (approximately 120 minutes) to the scheduled times after the infusion resulting in 125, 130, 140, 150, 180, and 240 minutes from the beginning of the infusion.

8.1.3 **PK Input File Creation**

The PK analysis dataset will be created from SBC-102 serum levels provided by the bioanalysis laboratory combined with study database records of the actual dose amounts and infusion start times and actual sampling times. The actual elapsed time for each sample will be calculated from the actual clock time of infusion start to the actual clock sample time. The actual clock time for each sample will be compared with the scheduled time for each sample to determine the time difference to be reported in minutes.

8.1.4 PK Serum Sample Presentations

PK concentration data will be listed as received from the bioanalytical laboratory along with dosing dates and times, scheduled sampling times, elapsed time from start of the infusion, lab reported concentration, and deviation from the scheduled sampling times in minutes.

PK concentration data will be summarized by dose at the time of the infusion (rather than cohort) and profile week (24, 52, and 104) using the modified sampling schedule times.

Observed values of SBC-102 concentrations will be summarized by dosing regimen and plotted over time. Descriptive statistics will include mean, SD, minimum, median, maximum, CV% and geometric mean. SBC-102 concentrations at pre-dose times will be set to zero and a footnote added if this situation occurs.

Figures will be provided for each subject's concentration-time data and for mean data at each dose and profile week. Individual concentration-time figures will contain Weeks 24, 52, and 104 profiles plotted in the same figure with origin for both lines being the start of the infusion. Mean concentrations will be illustrated in 3 figures (Weeks 24, 52, and 104) with different plots for different doses (since subjects may be changing doses during the study, there may be up to 3 dose levels. All figures will be presented in linear and semi-log scale.. Based on a review of the final data, some adjustments may be made to the graphical presentations and additional figures may be created to more fully present the data.

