8.9 Pharmacokinetics

 C_{max} and C_{min} will be recorded from direct observation, and other PK parameters will be derived by non-compartmental analysis. Pharmacokinetics will be characterized using the PK Analysis Set. All PK parameters will be summarized by dosing by dosing regimen.

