8.11 Missing or Invalid Data

All data will be analyzed as they were collected in the database. Missing data will not be imputed using statistical methods.

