8.2 Pharmacokinetic Parameters

Individual PK parameters will be computed for samples obtained for PK characterization (multiple-dose parameters at Weeks 24, 52, and 104/end of study). Profile intervals will begin at the time of the start of the infusion and continue to the last sample collected on that infusion period. PK parameters will be estimated by standard non-compartment analysis (NCA) methods.

A summary of calculated PK parameters will be presented. All SBC-102 concentrations and calculated PK parameters will be included in data listings. Descriptions and calculations of the PK parameters are presented in the table below.

Parameter	Unit	Description of Parameter	
C _{max}	ng/mI	The maximum serum level observed in units of concentration. Observed	
iig/iiiL		for each subject-dose profiled.	
t _{max}	hr	The time to reach the Cmax in hours to hundredths of the hour. Observed	
	111	for each subject-dose profiled.	
AUC0-t	hr×ng/mL	The Area Under the Concentration curve from the start of the infusion to the last measurable level at weeks 24, 52, and 104/end of study.	
	U	Trapezoidal rule used for estimation.	
AUCtau		The Area Under the Concentration curve from the start of the infusion to the end of the dosing interval.	
	hr×ng/mL	Trapezoidal rule used for estimation but with linear extrapolation to end	
		of dosing interval if needed.	
AUCO-∞		The Area Under the Concentration curve from the start of the infusion	
		extrapolated to infinity (∞) on Day 0.	
		AUC0-t + $[Ct/z]$ where Ct is the last measurable level of a profiled dose	
		interval.	
Z	1/hr	Apparent terminal rate constant calculated from the regression analysis (slope) from the log-transformed measured concentrations on the terminal phase of the time-point concentration curve.	
		Based on slope from linear regression of terminal phase.	
t½	1	Apparent terminal half-life.	
hr		$t^{1/2} = \ln(2)/z.$	
CL mL/hr/kg		Total body clearance.	
		CL =dose/AUC0-t (Weeks 24, 52, and 104/end of study).	
Vz	mI /ka	Volume of distribution after IV infusion.	
IIIL/Kg		Vz = MRTiv x CL where $MRTiv =$ mean residence time.	

Parameters for PK Analysis

For PK parameter estimation, analyte concentrations that are below the limit of quantification (BLQ) will be assigned a value of zero when they precede the first quantifiable sample. BLQ

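### The SAP's pre-dose rule, read literally, puts zeros in place of measured concentrations in the PK summaries and figures, and the protocol's Cmin is left out of the SAP parameter table without being declared

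*SAP*

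**What the plan says.** A pre-dose PK sample is scheduled at each PK visit (Protocol 5.1.12; SAP 8.1.1), with profiles at Weeks 24, 52 and 104.

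**Presentation of concentrations.** SAP 8.1.4 states that "Observed values of SBC-102 concentrations will be summarized by dosing regimen and plotted over time", and then that "SBC-102 concentrations at pre-dose times will be set to zero and a footnote added if this situation occurs". The same section also says that "PK concentration data will be listed as received from the bioanalytical laboratory along with dosing dates and times".

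**Parameter estimation.** SAP 8.2 has its own rule: "analyte concentrations that are below the limit of quantification (BLQ) will be assigned a value of zero when they precede the first quantifiable sample". It adds that "All SBC-102 concentrations and calculated PK parameters will be included in data listings".

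**General principle.** Protocol 8.11 says "All data will be analyzed as they were collected in the database", and SAP 5.3 repeats this.

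**Cmin.** The Protocol Synopsis and Protocol 3.2.2.5 name Cmin as a PK parameter. Protocol 8.9 says that Cmax and Cmin "will be recorded from direct observation, and other PK parameters will be derived by non-compartmental analysis". The SAP defines Cmin in its abbreviation list, but the parameter table in SAP 8.2 has no Cmin row. SAP Section 14 lists six changes from the protocol, and neither the loss of Cmin nor the pre-dose rule is among them.

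**The concern.** A programmer who follows the 8.1.4 sentence as written would enter zero for every pre-dose sample, whatever the laboratory reported. The tables and plots would then present as observed a value that nobody observed.

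The pre-dose sample has no substitute. The last sample of each profile is 120 minutes after the infusion ends, and the dosing interval is one or two weeks, so this is the only scheduled PK sample near the end of an interval. Protocol 1.3 anticipates a short plasma half-life, so a quantifiable pre-dose value would be unusual and worth seeing. Altered clearance, assay interference, or a sampling or dosing-time error are all possible explanations. The documents give no assay detail that would separate them. Protocol 3.2.2.5 wants the effect of anti-drug antibodies (ADAs) on PK assessed, and an unusual trough bears on that question.

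Cmin is a separate matter. Whatever 8.1.4 was meant to say, a parameter that the protocol requires would go unreported, with no record that it was dropped on purpose. Protocol Section 8 says the SAP will document changes, and SAP 4.3 says they are listed in Section 14.

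**Working it through.** The plan states no figure on this point, so there is none to reproduce. Steps 1 and 2 compare texts. Steps 3 to 5 are illustrations; their half-lives, background levels and concentrations are assumptions, not document figures.

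**1. The two zero rules**

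| | SAP 8.1.4 | SAP 8.2 |
|---|---|---|
| Use | summaries and figures | parameter estimation |
| Values set to zero | pre-dose, no BLQ condition | BLQ only, before the first quantifiable sample |
| Trigger | an undefined situation | stated |

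The scopes differ, so 8.2 does not settle what 8.1.4 means. The literal text of 8.1.4 covers quantifiable values.

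**2. Cmin**

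It is required in the Protocol Synopsis, 3.2.2.5 and 8.9, and defined in the SAP abbreviations. It is absent from the SAP 8.2 table and from the Section 14 list.

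**3. Expected true carry-over**

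The fraction of the end-of-infusion level left at the next dose is 2^(−(τ − 2)/t½). Here τ = 168 h (qw) or 336 h (qow), and the infusion lasts about 2 h (SAP 8.1.1).

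| Assumed t½ | qw | qow |
|---|---|---|
| 6 h | 4.7 × 10⁻⁷ % | 1.8 × 10⁻¹⁵ % |
| 24 h | 0.83% | 0.006% |
| 48 h | 9.1% | 0.80% |

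With a short half-life, nearly all pre-dose values should be BLQ. A quantifiable one would be unlikely to be ordinary carry-over.

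**4. Effect on a pre-dose summary**

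Take n = 9 (the maximum in Protocol 4.2), with seven BLQ values set to 0 and two values of 40 and 80 in arbitrary units.

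- As measured: mean = 120/9 = 13.3; SD = √[(8000 − 1600)/8] = 28.3; maximum 80; CV = 28.3/13.3 = 212%.
- All zeroed: mean 0, SD 0, maximum 0; CV is 0/0, undefined.

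SAP 8.1.4 says "Descriptive statistics will include mean, SD, minimum, median, maximum, CV% and geometric mean". The geometric mean is zero or undefined in both cases, because BLQ zeros remain, so that problem is not specific to the literal rule.

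**5. Effect on Cmin and AUC**

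Assume a one-compartment profile, a 2 h infusion, t½ of 0.1 to 2 h, the scheduled sampling times, and a constant background b of 0.01, 0.05 or 0.10 of Cmax.

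- Keeping the measured pre-dose value, Cmin = b, that is 0.01, 0.05 or 0.10 of Cmax.
- Zeroing it and counting it, Cmin = 0.
- Leaving the pre-dose sample out, the minimum is 0.01 to 0.25 of Cmax. It then comes from the 10-minute sample or the last post-infusion sample, which is not a trough.
- Zeroing the first point removes b × (10/60)/2 = b/12 (in Cmax × h) from AUC0-t. At b = 0.10 and t½ = 0.1 h this is 0.0083/2.39 = 0.35%, the largest change found. The smallest is 0.03%.

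Cmin depends entirely on how the pre-dose sample is treated, while AUC hardly moves.

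**The case against.** The best defence is that 8.1.4 is a presentation rule, drafted loosely, for BLQ pre-dose values. The situation that triggers the footnote is not defined, and the BLQ rule in 8.2 applies only to parameter estimation, so tables and plots needed a rule of their own. On that reading nothing measured is replaced. This is a possible reading, and it means one cannot argue that 8.1.4 must act only on quantifiable values because 8.2 already deals with BLQ ones. But the sentence does not say BLQ, and the SAP shows in 8.2 that it can. If BLQ was meant, the same edit cures it.

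The second defence is that nothing is lost. That is right for the listings: values appear as received, all concentrations are listed again under 8.2, and the zeroing carries a footnote. With at most 27 scheduled pre-dose values, a reader could find a non-zero one. A reader might infer that carry-over or assay interference would be hidden; the listings contradict that.

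A reader might also infer that Cmin becomes zero by construction. The documents do not support this. A Cmin missing from the table is not reported at all. It would be zero only if it were derived from the zeroed presentation data with the pre-dose sample counted. The SAP says neither, its estimation rule zeroes only leading BLQ values, and its profile interval begins at the start of the infusion.

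Finally, these are descriptive analyses with no formal hypothesis tests (Protocol 8.10.1), and Cmax, AUC, clearance and half-life are unaffected or nearly so. This limits the importance of the point. It does not answer the undeclared omission of Cmin.

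**Conclusion.** The point holds in two parts. First, SAP 8.1.4 as written allows measured pre-dose concentrations to be replaced by zero in summaries and figures. That contradicts the observed-value summaries promised in the same section and the as-collected principle, and it is inconsistent with the BLQ-only rule in 8.2. Second, Cmin is a protocol PK parameter that the SAP does not plan to report, and the change is not declared. The second part does not depend on how 8.1.4 is read.

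The size is modest. The first part touches the pre-dose row of the summaries and the pre-dose point of the figures, and matters only if some pre-dose values are quantifiable. If the half-life is short, as the protocol anticipates, few or none should be. The effect on AUC0-t is negligible (0.03% to 0.35% under the assumed half-lives and backgrounds), and it is nil if the 8.1.4 rule never enters parameter estimation. The source values remain in the listings throughout.

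**What to change.** 1. Replace the sentence in SAP 8.1.4 with: *Pre-dose concentrations are summarised as measured; only BLQ pre-dose values are set to zero, with quantifiable pre-dose values footnoted.*
2. Restore Cmin to the parameter table in SAP 8.2, defined as the observed pre-dose (trough) concentration and summarised by regimen and profile week. The definition should name the pre-dose sample, since a minimum over the other samples is not a trough.
3. In the same edit, say how the geometric mean is handled when some values are zero.

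Showing ADA status beside quantifiable pre-dose values would be useful but is optional, because the ADA results are listed anyway.

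The cost is a few lines of SAP text and one table row. The samples are already scheduled, and no new data are needed.
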